**Criteria for discontinuing study intervention includes but not limited to:**

- Allergic reaction thought to be related to study drug.
- Uncontrolled hypertension, hypotension, or arrhythmia thought to be related to study drug.
- Severe psychomimetic side effects.
- Medical events/logistical reasons not related to study therapy.

Study physician will be responsible for determining whether study interventions will be discontinued, based on his or her clinical judgement. In the case of cardiovascular side effects, if such side effects persist despite treatment based on PACU clinician's decisions, study drug may be discontinued. The reason for the dose discontinuation should be documented.

Psychomimetic side effects will be monitored by study and PACU physicians. Such side effects may be treated with reassurance. If participants continue to complain of anxiety or dysphoria or are agitated, pharmacologic agents (such as benzodiazepines) may be administered based on clinical judgement of PACU clinicians. If psychomimetic side effects are felt to be severe, with severe hallucinations, delusions, or agitation, study drug will be discontinued.

Additionally, in the event of any discontinuation of study intervention, with consent, participants will continue with the completion of remaining study visits.

**4.7.2 Handling of Participant Withdrawals or Termination**

CONFIDENTIAL

This material is the property of the NYU School of Medicine and Langone Medical Center. Do not disclose or use except as authorized in writing by the study sponsor

Subjects, who choose to withdraw consent, can do so by notifying the treating physician, the Principal Investigator or research staff in writing or verbally. Any data remaining after formal withdrawal, will be destroyed/discharged per Institutional guidelines. Subject will be informed whether the data will be retained and analyzed up to the point of withdrawal. The study team will document the reason for discontinuation in the subjects' research record. Every effort will be made to undertake protocol-specified safety follow-up procedures to capture AEs, serious adverse events (SAEs), and unanticipated problems (UPs). If subjects withdraw or discontinue early replacement participants will be allowed.

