### **1.3.1 Protection against Risks**

Given that ketamine will be given in the recovery room, all participants will be monitored by the study care team and PACU physicians, if any of these effects mentioned above were to occur. For the risks of physiological effects and cardiovascular side effects, the single bolus ketamine dose will be given over at least a 30-minute period to minimize these effects from happening. For the risks of psychomimetic side effects, such side effects may be treated with reassurance.

The investigators have many layers of protection to minimize the risk of inadvertent release of protected health information. The methods for de-identification of data will mitigate this risk. We will take all necessary precautions to maintain complete confidentiality of data and prevent unauthorized access to the data. Data will only be collected from subjects who consent and whose physicians deem safe to proceed with data collection. Participants will be allowed to exit the study at any time. Participants who withdraw consent will be counseled that their withdrawal only affects uses and sharing of information after their written request to withdraw authorization has been received, and that their authorization may not be withdrawn for uses or disclosures that have previously made or need to be made to complete analyses or report data from the research. For the confidentiality of randomization, only the physician administering the study drug will know which group the subject(s) is/are in for the both experimental and control group.

All data and records generated during this study will be kept confidential in accordance with institutional policies and HIPAA on subject privacy. The study investigators will not use such data and records for any other purpose other than conducting the study. Privacy protection procedures are in place and good clinical practice guidelines will be followed throughout the study to minimize the risks associated with breach of confidentiality. This risk will be minimized by strict compliance with HIPAA procedures for securing PHI.

CONFIDENTIAL

This material is the property of the NYU School of Medicine and Langone Medical Center. Do not disclose or use except as authorized in writing by the study sponsor

Information that could be used to identify the subject will only be shared with researchers who have approval of the IRB.

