### **3 Study Design and Endpoints**

#### **3.1 Description of Study Design**

This is a randomized, single-blind, placebo-controlled, two-arm parallel, single-center study.

Thirty subjects (15 in each arm) will be accrued. Randomization lists will be sent only to the study physician administering study drug. Participant and assessor of outcome measures will be blinded. The surgeon, anesthesiologist, and the research team members conducting the follow up visits will not know which group the subjects are assigned to. The physician administering the study will be aware of whether ketamine or placebo is administered. On the day of the mastectomy surgery, the subject will be randomly assigned to the control or the experimental group.

Adult women who will be undergoing mastectomy will be screened for eligibility to participate in the study. Prospective subjects will be recruited, screened and consented prior to surgery. Eligible subjects will be randomized to one of the two groups in a 1:1 ratio to receive either intravenously (IV) ketamine (0.6mg/kg) or matching equal dose of placebo. Only women will be recruited in this study, as mastectomies are primarily done in women. As men represent less than 1% of breast cancer cases and mastectomy may have a different psychosocial impact on them, we will only enroll women for this study. There is no limitation as to racial and ethnic origin.

Participation in the study will not alter the subject's surgical or anesthetic care, post-anesthetic care, or standard of care on the floor. In the PACU, subjects, if deemed medically stable by the study physician, will receive equal dosage of 0.6mg/kg IV ketamine or saline placebo. All subjects will also receive standard post-anesthetic monitoring and care, as well as routine care after transfer out of the PACU. There is no restriction on the use of other analgesics throughout this study. Subjects are followed, and endpoints (see

CONFIDENTIAL

This material is the property of the NYU School of Medicine and Langone Medical Center. Do not disclose or use except as authorized in writing by the study sponsor

below) are collected from subject reports as well as from medical charts (opioid use). During the study, subjects will fill out self-reported questionnaires assessing pain, mood (fatigue) and function (physical), side effects, and quality of postsurgical recovery including sleep quality.

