### **13.5 Participant and Data Confidentiality**

Information about study subjects will be kept confidential and managed according to the requirements of the Health Insurance Portability and Accountability Act of 1996 (HIPAA). Those regulations require a signed subject authorization informing the subject of the following:

- What protected health information (PHI) will be collected from subjects in this study
- Who will have access to that information and why
- Who will use or disclose that information
- The rights of a research subject to revoke their authorization for use of their PHI.

In the event that a subject revokes authorization to collect or use PHI, the investigator, by regulation, retains the ability to use all information collected prior to the revocation of subject authorization. For subjects that have revoked authorization to collect or use PHI, attempts should be made to obtain permission to collect at least vital status (i.e. that the subject is alive) at the end of their scheduled study period.

Participant confidentiality is strictly held in trust by the participating investigators, their staff, and the sponsor(s) and their agents. This confidentiality is extended to cover testing of biological samples and genetic tests in addition to the clinical information relating to participants. Therefore, the study protocol, documentation, data, and all other information generated will be held in strict confidence. No information concerning the study or the data will be released to any unauthorized third party without prior written approval of the sponsor.

The study monitor, other authorized representatives of the sponsor, representatives of the IRB or pharmaceutical company supplying study product may inspect all documents and records required to be maintained by the investigator, including but not limited to, medical records (office, clinic, or hospital) and pharmacy records for the participants in this study. The clinical study site will permit access to such records. The study participant's contact information will be securely stored at each clinical site for internal use during the study. At the end of the study, all records will continue to be kept in a secure location for as long a period as dictated by local IRB and Institutional regulations.

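### Section 4.7.2 can be read as destroying data collected before withdrawal, against sections 1.3.1, 13.5 and 14.2, and with open-ended replacement this could bias the primary comparison

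*Combined protocol and SAP*

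**What the plan says.** Section 4.7.2 (Handling of Participant Withdrawals or Termination) contains three sentences that matter here:

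- On data: "Any data remaining after formal withdrawal, will be destroyed/discharged per Institutional guidelines".
- On what the participant is told: "Subject will be informed whether the data will be retained and analyzed up to the point of withdrawal".
- On numbers: "If subjects withdraw or discontinue early replacement participants will be allowed".

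Three other sections bear on the same data:

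- Section 1.3.1, speaking of participants who withdraw consent, says they will be counselled that "their withdrawal only affects uses and sharing of information after their written request to withdraw authorization has been received". It adds that authorization cannot be withdrawn for past uses or for those that "need to be made to complete analyses or report data from the research".
- Section 13.5 says that after a revocation the investigator "retains the ability to use all information collected prior to the revocation of subject authorization".
- Section 14.2 (Study Records Retention) keeps study documents for years, requires the sponsor's written consent, where applicable, before any record is destroyed, and keeps de-identified information indefinitely.

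Section 10 and its SAP subsection define no analysis population and give no rule for withdrawals or missing data. Section 4.6 expects about 50 enrolled to give 30 evaluable participants and does not define evaluable.

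**The concern.** The destruction sentence does not say what the remaining data are. It could mean anything left over that is not to be kept, or everything on file for that participant. The next sentence does not settle it, because it promises only to tell the participant whether her data are kept. Staff working from section 4.7.2 alone could delete a valid 24-hour score from someone who withdraws on postoperative day 2 and enrol another participant in her place. Deletion cannot be undone.

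At stake is the randomised comparison. If those who withdraw differ in pain from those who stay, and withdrawal differs by arm, erasing their scores makes the arms non-comparable. The planned mixed model can use a 24-hour score when the 48-hour score is missing, but only if that score still exists. With 15 per arm, two or three participants are enough to matter.

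**Working it through.** **The texts side by side**

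| Section | Trigger | Data from before withdrawal |
|---|---|---|
| 4.7.2 | Withdrawal of consent, written or verbal | Undecided; can be read as destroyed |
| 1.3.1 | Withdrawal of consent; counts from a written request | Usable, including to complete analyses |
| 13.5 | Revocation of authorization | Usable |
| 14.2 | Any destruction of records | Needs sponsor's written consent, if applicable |

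Two sections decide the question in favour of keeping the data, one restricts destruction, and section 4.7.2 leaves it open. The triggers differ too: a verbal withdrawal counts in section 4.7.2, while section 1.3.1 dates the effect from a written request.

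**Who can be affected.** Randomisation is on the day of surgery, so some withdrawals come before it and do no harm to the comparison. A participant who leaves after randomisation but before 24 hours has no primary score to lose. The exposed group is those who formally withdraw consent after a 24-hour score exists.

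**The plan's own figure.** The sample-size section states 80% power for an effect size of 1.1 with 15 per arm (two-sided Wilcoxon rank-sum test, alpha 0.05, normal data). Simulation with the exact null distribution gives 79.6%. The figure reproduces, and this point does not depend on it.

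**Size of a selective loss (assumed)**

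Inputs: 15 per arm, the Wilcoxon test, two-sided alpha 0.05 and normal data, all from the plan. Assumptions: no true effect; the k highest pain scores in one arm are the ones erased; any replacement is a random new participant in the same arm.

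The expected three largest values of 15 standard normal scores are 1.736, 1.248 and 0.948. Let S be the sum of the top k: 1.736, 2.984 and 3.932 for k = 1, 2, 3. Erasing them shifts the arm's mean by −S/(15 − k). Erasing and replacing them shifts it by −S/15.

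| k | Shift, erased (SD) | Shift, erased and replaced (SD) | Error rate, erased | Error rate, erased and replaced |
|---|---|---|---|---|
| 1 | 1.736/14 = 0.12 | 1.736/15 = 0.12 | 6.2% | 6.1% |
| 2 | 2.984/13 = 0.23 | 2.984/15 = 0.20 | 9.5% | 8.5% |
| 3 | 3.932/12 = 0.33 | 3.932/15 = 0.26 | 14.1% | 11.2% |

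The error rates are from 200,000 simulated trials per row, using the exact test, whose own size at 15 v 15 is 4.6%. Replacement restores the number in the arm and reduces the bias, but does not remove it.

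**The case against.** The strongest reply is that section 4.7.2 does not order deletion of earlier data. Its next sentence contemplates retention and analysis up to withdrawal, and the remaining data can mean whatever lies outside that retained set. This stands. A reader might infer that the section flatly destroys pre-withdrawal data, and the text does not support that. What it supports is ambiguity within the section and a conflict with three others on one of its readings.

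Second, the other sections largely answer the question. They do, but section 4.7.2 is the one that governs withdrawal. The safeguard in section 14.2 is qualified by its own condition, and sections 1.3.1 and 13.5 are framed around authorization to use information, although section 1.3.1 does name withdrawal of consent. The consent form is not available for this review and may already settle the matter.

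Third, a reader might infer that ketamine side effects will drive selective loss. The documents do not show this. They give no withdrawal rates or reasons by arm. Stopping the infusion is not withdrawal: "in the event of any discontinuation of study intervention, with consent, participants will continue with the completion of remaining study visits", and section 6.1.4 has participants told that they may stop the drug and stay in the study. Side effects need not pick out those with most pain, and poor relief could prompt withdrawal in either arm.

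Fourth, the trial is a pilot that says it is not powered for a hypothesised effect. That lowers the stakes of a single test result, but a biased estimate would still mislead whatever is planned from it.

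**Conclusion.** The concern holds as an unresolved conflict with a conditional consequence. Section 4.7.2 can be read as erasing data that sections 1.3.1 and 13.5 keep. Replacement is not confined to withdrawals before randomisation, and the plan has no analysis-set or missing-data rule that would prevent an erase-and-replace.

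If that reading were followed, and the 1, 2 or 3 highest-pain participants in one arm were lost and replaced, the false difference would be about 0.12, 0.20 or 0.26 SD and the error rate about 6%, 8% or 11%. Without replacement the error rate would be about 6%, 9.5% or 14%. These figures assume the worst possible selection for each k, all in one arm, and refer to the Wilcoxon comparison rather than the mixed model. Weaker dependence on pain, or losses spread over both arms, would give less. It cannot be concluded that the primary comparison is or will be biased, only that the wording permits it. The stated 80% power is not in question.

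**What to change.** Reword section 4.7.2 to agree with sections 1.3.1, 13.5 and 14.2. For example: on withdrawal of consent, further collection of research data stops; data collected before withdrawal are retained and analysed in the arm to which the participant was randomised, including when a replacement is enrolled. The section's existing sentence on safety follow-up can stay as it is.

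Use one trigger for withdrawal, written or verbal, in sections 4.7.2 and 1.3.1, and check that the consent form says the same.

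The cost is a sentence or two and a check of the consent form. The target of 15 per arm and the power statement do not change. If replacements are enrolled, an arm may hold slightly more than 15 randomised participants in the analysis.

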#### **4.8 Premature Termination or Suspension of Study**

This study may be temporarily suspended or prematurely terminated if there is sufficient reasonable cause. If the study is prematurely terminated or suspended, the PI will promptly inform the IRB and will provide the reason(s) for the termination or suspension.

Circumstances that may warrant termination or suspension include, but are not limited to:

- Determination of unexpected, significant, or unacceptable risk to participants.
- Demonstration of efficacy that would warrant stopping.
- Insufficient compliance to protocol requirements.
- Data that are not sufficiently complete and/or evaluable.
- Determination of futility.

Study may resume once concerns about safety, protocol compliance, data quality are addressed and satisfy the sponsor, IRB and/or FDA.

### **5 Study Agent/Procedural Intervention**

#### **5.1 Study Agent(s) and Control Description**

Ketamine is an FDA-approved general anesthetic and analgesic agent that has been safely used clinically over the last 50 years. For general anesthesia, the intravenous induction doses range from 1 mg/kg to 4.5mg/kg. At subanesthetic doses (<1mg/kg), ketamine is a potent analgesic with a clinically effective half-life of 45 min. Off label it is also used as a powerful antidepressant and anxiolytic as a single dose (0.3-0.6mg/kg) which can produce up to 14 days of mood stabilization.

This study is IND exempt as 21 CFR 312.2(b)(1) and 21 CFR 312.2(b)(5) as the study meets the all of the following criteria:

1. The drug product is lawfully marketed in the US.
2. The investigation is not intended to be reported to FDA as a well-controlled study in support of new indication and there is no intent to use it to support any significant change in the labeling of the drug.
3. In the case of a prescription drug, the investigation is not intended to support a significant change in the advertising for the drug.
4. The investigation does not involve a route of administration, dose, patient population, or other factor that significantly increase the risk (or decreases the acceptability of the risk) associated with the use of the drug product.
  - a. The risks for ketamine are well studied. In general, ketamine is a well-tolerated medication. In previous studies for depression and pain, a dose range of 0.3-0.6 mg/kg was used. In our prior study of ketamine for bariatric surgery, we used 0.4 mg/kg for ideal body weight. To further evaluate a single dose of ketamine for postoperative pain, we will use 0.6 mg/kg, which is in the range of the therapeutic dose for mood disorders and pain.
5. The investigation is conducted in compliance with the requirements for review by an IRB and with the requirements for informed consent.
6. The investigation is conducted in compliance with 21 CFR 312.7 (no intention to promote or commercialize the drug product).

##### **5.1.1 Acquisition**

Study drug will be ordered and obtained from NYULH inpatient pharmacy.

CONFIDENTIAL

This material is the property of the NYU School of Medicine and Langone Medical Center. Do not disclose or use except as authorized in writing by the study sponsor

### **5.1.2 Formulation, Appearance, Packaging, and Labeling**

Ketamine is a nonbarbiturate general anesthetic chemically designated dl 2-(0-chlorophenyl)-2-(methylamino) cyclohexanone hydrochloride. It is formulated as a slightly acid (pH 3.5-5.5) sterile solution for intravenous or intramuscular injection. Ketamine is available from NYULH inpatient pharmacy in concentrations of 50 mg/ml.

### **5.1.3 Product Storage and Stability**

The study drug should be stored between 20° to 25°C (68° to 77°F).

The control solution, 0.9% normal saline will be stored at temperatures between 20° 25°C (68° to 77°F).

### **5.1.4 Preparation**

Study drug is obtained from NYULH inpatient pharmacy [contact]). Study physician is not blinded. Ketamine will be diluted to 2-10 mg/ml in normal saline by study physician. 0.9% normal saline will be used as the control.

### **5.1.5 Dosing and Administration**

**Single bolus ketamine:** For the single bolus dose arm, ketamine at a dose of 0.6 mg/kg will be administered while the participant is recovering in the PACU on the day of surgery. The study drug will be administered over at least 30 minutes at one time point and will be administered after subject has been deemed to be stable (hemodynamically stable, awake) by the study team on POD 0.

**Control/Placebo:** Participants randomized into this group will receive matching volume of saline infusion in the PACU over at least 30 minutes at one time point (no ketamine).

**5.1.5.1 Route of Administration:** The planned route of administration is intravenously for the ketamine study drug and placebo drug.

#### **5.1.5.2 Tracking of Dose:**

Drug protocol adherence will be recorded and verified through patient's electronic medical record.

#### **5.1.5.3 Administration of Intervention**

The intervention will be delivered in person at NYULH. The study physician will administer the study intervention via a pump to deliver 0.6 mg/kg ketamine or equal volume saline over at least 30 minutes.

#### **5.1.5.4 Procedures for Training Interventionists and Monitoring Intervention Fidelity**

Study drug will be administered by study physicians who are anesthesiologists or pain medicine specialists. Protocol and study procedures will be reviewed with study team members and study physicians.

#### **5.1.5.5 Assessment of Subject Compliance with Study Intervention**

Subject compliance with receiving the study drug will be recorded in subjects' records.

### **5.1.6 Study Agent Accountability Procedures**

Study drug will be ordered by study physician when participant arrives to PACU. Regular study drug reconciliation will be performed to document drug assigned, drug consumed, and drug remaining. Controlled substance disposal procedures will be followed per pharmacy procedure.

## **6 Study Procedures and Schedule**

### **6.1 Study Schedule**

#### **6.1.1 Screening**

CONFIDENTIAL

This material is the property of the NYU School of Medicine and Langone Medical Center. Do not disclose or use except as authorized in writing by the study sponsor

